8.4 Secondary safety outcomes

Asymptomatic intracerebral hemorrhage (aSICH);

Large cerebral infarction or surgical intervention for intracerebral hemorrhage;

Complications excluding intracerebral hemorrhage (including gastrointestinal bleeding, urethral bleeding, oral or nasal mucosal bleeding, and subcutaneous hematomas);

Non-hemorrhagic severe adverse events (including brain herniation, pneumonia, respiratory failure, circulatory failure, stress ulcers, secondary epilepsy, urinary tract infections, sepsis, renal failure, acute coronary syndrome, venous thromboembolism, and psychiatric symptoms);

Procedure- or device-related complications (including arterial rupture, arterial dissection, complications at the vascular puncture site, and vasospasm).

9. Statistical analysis

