collateral circulation compared to embolic stroke patients [21-23]. Studies have indicated that blood pressure variability following vascular recanalization is linked to prognosis in patients with poor collateral circulation, but not in those with good collateral circulation [24-26]. Thus, patients with embolic strokes may be more susceptible to the effects of blood pressure. A recent study confirmed this view by analyzing blood pressure data from 147 patients with atherosclerotic stroke and 273 patients with cardioembolic stroke [27]. The study found that in patients with cardioembolic stroke, greater blood pressure variability within 24 hours after endovascular therapy was associated with a lower risk of functional independence at 3 months and a higher risk of cerebral hemorrhage. However, these correlations were not observed in patients with atherosclerotic stroke [27]. After acute ischemic stroke, impaired cerebral autoregulation makes blood flow in penumbra highly sensitive to blood pressure [28]. Elevated blood pressure can increase cerebral perfusion pressure and induce microvascular dilation, which may trigger microvascular spasm, further damage the blood-brain barrier, and convert ischemic vessels into channels for cerebral edema and hemorrhagic transformation [15, 29]. Conversely, excessively low blood pressure can result in inadequate cerebral blood flow, causing hypoperfusion, enlarging the infarct, and contributing to a poor prognosis [30]. After endovascular thrombectomy, patients with large-artery atherosclerotic stroke often have residual stenosis. Intensive blood pressure control in these patients may lead to hypoperfusion and exacerbate ischemic symptoms, thus blood pressure should be maintained at a relatively higher level. In contrast, for patients with embolic stroke, as there is no residual stenosis in the vessels, the primary concern after vascular recanalization is preventing hyperperfusion-related hemorrhagic transformation, and blood pressure should be kept at a relatively lower level. Compared to patients with large artery atherosclerotic stroke, those with embolic stroke may require more stringent blood pressure management. Previous studies that directly pooled patients with different stroke etiologies may have masked the impact of blood pressure on prognosis.

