8.2 Primary safety outcomes

Rate of symptomatic intracranial hemorrhage (sICH), defined by the Heidelberg Bleeding Classification criteria [31];

All-cause mortality at 3 months.

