8.3 Secondary efficacy outcome

mRS score 0–1 at 90 days;

mRS score 5–6 at 90 days;

Functional recovery, defined by 90-day mRS score improvement (shift analysis);

Infarct volume at 24 hours;

Change in infarct volume at 24 hours (compared to baseline);

NIHSS score at 24 hours;

Change in NIHSS score at 24 hours (compared to baseline);

24-hour NIHSS score 0–1 or improvement >8 points (%);

Change in NIHSS score at 7 days;

Brain edema volume at 7 days;

Health-related quality of life at 90 days (assessed by EQ-5D score).

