9.2 Statistical analysis methods

For continuous variables that follow a normal distribution, data will be presented as mean \pm standard deviation. For continuous variables that do not follow a normal distribution, data will be presented as median and interquartile range. Between-group comparisons will be performed using the independent t-test or Mann-Whitney U test. Categorical or ordinal data will be summarized using frequencies and percentages. For comparisons of categorical data between two groups, the χ^2 test or Fisher's exact test will be used; for ordinal data, the Mann-Whitney U test will be applied. All statistical analyses will be performed using SPSS software. A p-value < 0.05 will be considered statistically significant.

10. Study steps

After preliminary screening, patients who meet the criteria for endovascular intervention will undergo the procedure. Endovascular treatment methods include mechanical thrombectomy and aspiration.

[figure not shown]
At the end of the endovascular procedure, angiography will be used to assess successful reperfusion of the occluded vessel without in-situ or proximal arterial stenosis, with mTICI \geq 2b. Additionally, the patient's systolic blood pressure will be continuously elevated (\geq 140 mmHg, maintained for >10 minutes).

Randomization.

The intensive blood pressure control group will receive more intensive blood pressure management (target systolic blood pressure of 120 mmHg, achieved within 1 hour and maintained for 48 hours). The less intensive blood pressure control group will not have strict blood pressure control (target systolic blood pressure of 140-180 mmHg).

Follow-up and data collection.

11. Study schema

[figure not shown]

Figure 1. Study schema

12. Schedule of evaluations

Evaluation	Baseline (Prior randomisation)	Treatment phase		Follow-up phase
		1 day	7 days ^a	
Consent	X			
Eligibility	X			
Basic information	X			
Medical history	X			
Blood pressure	X	X	X	
mRS	X		X	X
NIHSS	X	X	X	
ASPECTS	X			
EQ-5D				X
Blood tests	X			
Menstrual history/urine pregnancy test (female)	X			
Electrocardiogram	X			
Details of rt-PA (if performed) and endovascular thrombectomy	X			
Brain imaging (CT ± CTA/MRI±MRA/DSA)	X	X	X	
BP lowering treatment		X	X	
Standard stroke care		X	X	X

SAEs	X	X	X	X
Complications		X	X	X
Completion status of research				X

Table 1. Experimental procedures and items to be assessed at each time point

a: Or the day of discharge (if the patient is discharged before day 7).

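### Section 8.4 combines large infarction and surgery for haemorrhage in one safety outcome, so the combined count can understate an excess of large infarction on that line

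*Protocol*

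**What the plan says.** Protocol section 8.4 (Secondary safety outcomes) gives "Large cerebral infarction or surgical intervention for intracerebral hemorrhage" as one item. It does not say what counts as a large infarction, over what period events are counted, or whether surgery is meant to apply to both conditions.

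The background paragraph on stroke aetiology describes both directions of effect. Elevated pressure may "further damage the blood-brain barrier, and convert ischemic vessels into channels for cerebral edema and hemorrhagic transformation". In the other direction, "excessively low blood pressure can result in inadequate cerebral blood flow, causing hypoperfusion, enlarging the infarct, and contributing to a poor prognosis". For embolic stroke, the population of this trial, the same paragraph says that "the primary concern after vascular recanalization is preventing hyperperfusion-related hemorrhagic transformation".

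Section 9.2 gives the method that would apply to a yes/no outcome of this kind: "For comparisons of categorical data between two groups, the χ^2 test or Fisher's exact test will be used".

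Related outcomes are listed separately:
- Section 8.2: "Rate of symptomatic intracranial hemorrhage (sICH), defined by the Heidelberg Bleeding Classification criteria", and 3-month all-cause mortality.
- Section 8.3: infarct volume at 24 hours and its change from baseline, and oedema volume at 7 days.
- Section 8.4: asymptomatic intracerebral haemorrhage.

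**The concern.** A composite helps when its parts are expected to respond to treatment in the same way, because the added events then add information. Here the protocol's own mechanism allows the parts to respond in opposite ways. Lowering pressure may prevent some haemorrhages that need surgery, and if it goes too far it may enlarge some infarcts. A patient with either event counts once, so fewer operations in the intensive arm would offset more large infarctions, and the difference on this line would shrink towards zero.

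Section 2 sets out to study safety as well as efficacy. The background also reports two earlier trials in which intensive targets gave worse 3-month function without a significant difference in symptomatic haemorrhage. Harm that is not haemorrhagic is therefore a live question, and a safety line that could show it should not net it against a haemorrhagic benefit.

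The wording is also open to two readings, large infarction itself or surgery for large infarction, so sites could count different events.

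**Working it through.** **Plan's own figure.** The protocol states no rate or power for this outcome. Its sample size (section 5) fixes the number per group. With 35% v 45%, two-sided 0.05, 80% power and pooled variance under the null:

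n = [1.960 × √(2 × 0.40 × 0.60) + 0.842 × √(0.35 × 0.65 + 0.45 × 0.55)]² / 0.10² = 375.6, rounded up to 376.

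This reproduces the stated 376 per group.

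**Inputs**
- n = 376 per group and two-sided 0.05, from section 5.
- Component rates: assumed, because the protocol gives none. Large infarction is held at 8% control v 12% intensive, and the fall in surgery for haemorrhage is varied from small to fully offsetting.
- Non-overlapping components, so the composite rate is the sum: assumed for simplicity.

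**Formula.** With p̄ the mean of the two rates, Δ their difference, SE₀ = √[2p̄(1−p̄)/n] and SE₁ = √[(p₀(1−p₀) + p₁(1−p₁))/n]:

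power = Φ[(|Δ| − 1.96 SE₀)/SE₁] + Φ[(−|Δ| − 1.96 SE₀)/SE₁].

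**Infarction alone, 8% v 12%.** p̄ = 0.10, SE₀ = √(0.18/376) = 0.0219, SE₁ = √(0.1792/376) = 0.0218. (0.04 − 0.0429)/0.0218 = −0.13, so power is about 45%.

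**Composite, 12% v 15%** (surgery 4% v 3%). p̄ = 0.135, SE₀ = 0.0249, SE₁ = 0.0249. (0.03 − 0.0488)/0.0249 = −0.76, so power is about 23%.

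**Range at 376 per group**

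| Infarction, control v intensive | Surgery, control v intensive | Composite | Power: infarction alone | Power: surgery alone | Power: composite |
|---|---|---|---|---|---|
| 8% v 12% | 4% v 3% | 12% v 15% | 45% | 12% | 23% |
| 8% v 12% | 4% v 2% | 12% v 14% | 45% | 36% | 13% |
| 8% v 12% | 6% v 2% | 14% v 14% | 45% | 80% | 5% (false-positive rate) |

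In all three rows the composite has less power than the infarction component alone. Cancellation is complete only when the two shifts are equal. With the smallest offset, a 3-point excess still shows in the estimate. At 455 per group, the enrolment target, the composite figures are 26%, 15% and 5%, against 52% for infarction alone.

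**Opposite case.** If both parts fell in the intensive arm, say 8% v 5% (39% power) and 4% v 2% (36%), the composite of 12% v 7% would have 65%. Whether combining helps or hurts depends on whether the parts move together, and the protocol does not settle that.

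**The case against.** Four objections carry weight.

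1. A reader might infer that the protocol expects the two events to move in opposite directions, with large infarction as the main expected harm of the intensive arm. The text does not go that far. It ties infarct growth to excessively low pressure, and it raises the hypoperfusion risk of intensive control for atherosclerotic patients with residual stenosis, whom sections 4.1 and 4.2 leave out. For embolic stroke it names haemorrhage as the primary concern, and section 7.1 warns against hypotension. Opposite movement is a possibility in the protocol's reasoning, not a prediction. This objection stands, and the point needs only the possibility.

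2. The line may mean surgery for large infarction or for haemorrhage. It is tempting to say that the same opposition would then apply, but the documents do not support that. The background also links high pressure to oedema, a plausible reason for surgery after a large infarct, so both indications could fall together and combining them could help. This stands, and it is why the meaning must be settled first.

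3. The signals are captured elsewhere: haemorrhage in sections 8.2 and 8.4, infarct volume and oedema volume in 8.3, and mortality in 8.2. This stands as a limit on severity. It does not make the line itself informative: infarct volume is an efficacy measure at 24 hours, whereas section 7.1 maintains the target for at least 48 hours.

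4. Other lines in 8.4 are grouped headings too, and component tables are commonly left to a statistical analysis plan, which is not at hand. The absence of component tables is therefore no finding. What section 8.4 does fix is the composition of the outcome and its ambiguous wording.

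**Conclusion.** The point holds, and it is minor. On the literal reading, section 8.4 sums an ischaemic and a haemorrhagic event that pressure lowering could move in opposite directions, so the combined count can understate an excess of large infarction. With infarction assumed at 8% v 12% and 376 per group, power falls from 45% for that component to between 23% and 5% for the composite as the offset grows from 1 to 4 percentage points.

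These figures rest on assumed, non-overlapping rates and show a range, not a forecast. Separating the parts would not make the infarction comparison well powered either, at 45%. The gain is an estimate that means one thing.

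A reader might conclude that the trial as a whole could hide harm from infarction. The documents do not support that, because symptomatic haemorrhage, mortality, infarct volume and oedema volume are each outcomes in their own right. The masking is confined to this line.

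**What to change.** 1. In section 8.4, state whether the line means large cerebral infarction itself or surgery for it.
2. Replace it with two outcomes. On the first meaning: large cerebral infarction, and surgical intervention for intracerebral haemorrhage. On the second: surgery listed by indication, ischaemic and haemorrhagic.
3. Give each outcome a definition and a time window, and report each by arm with a risk difference and confidence interval.
4. A combined count may be kept, but only as a supplement to the two components.

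The cost is a few lines of protocol wording and one extra table row. The downside is fewer events per line, so each estimate is less precise. No treatment rule or visit changes; each component must be recorded so that it can be counted separately.

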9.1 Statistical analysis populations

Intention-to-Treat (ITT) Population: This population will include all randomized patients, regardless of whether they receive the intended intervention. A modified ITT analysis will be conducted based on the principle of the closest approach to the ITT population. Patients who withdraw consent before the blood pressure intervention, do not undergo the assigned procedure after randomization, lack endpoint data, refuse follow-up, or are lost to follow-up will be excluded from the statistical analysis. The modified ITT analysis will be used to evaluate the effectiveness and safety of the treatment regimen.

Per-Protocol (PP) Population: This population will exclude all patients with significant protocol violations, such as those who are under 18 years of age, have a final diagnosis other than acute ischemic stroke, have sustained systolic blood pressure <140 mmHg post-surgery, do not achieve reperfusion (mTICI <2b), have a pre-stroke mRS score of 3-5, lack 3-month follow-up data, or do not achieve the expected blood pressure control. The PP analysis will serve as a supplement to the modified ITT analysis.

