Therefore, we proposed a multicenter randomized controlled trial to investigate the impact of early intensive blood pressure control on the prognosis of patients with embolic stroke after successful reperfusion following endovascular thrombectomy.

2. Objectives

To investigate the safety and efficacy of intensive blood pressure control after successful

reperfusion following thrombectomy in patients with acute anterior circulation large artery embolic stroke.

3. Design

The study employs a multicenter, prospective, randomized, endpoint-blinded, parallel-controlled trial design. Patients with acute anterior circulation large artery occlusive stroke, who receive successful reperfusion after endovascular thrombectomy within 4.5 or 6.0 hours of onset, without significant in-situ or proximal vessel stenosis, and with sustained elevated systolic blood pressure (≥ 140 mmHg for >10 minutes), will be enrolled according to the clinical inclusion and exclusion criteria. The enrolled patients will be randomly assigned to the experimental group or control group (1:1). The experimental group will undergo intensive blood pressure management (target systolic pressure <120 mmHg, achieved and maintained within 1 hour for 48 hours), while the control group will have less intensive blood pressure control (target systolic pressure 140-180 mmHg). Patients will be followed up for 3 months to assess their prognosis.

4. Patient selection

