7.1. Intensive blood pressure control group (experimental group)

The target blood pressure is <120 mmHg within 1 hour after randomization, and this level should be maintained for at least 48 hours. Intravenous antihypertensive treatment should begin immediately after randomization. A systolic pressure of 100 mmHg is the threshold for discontinuing both antihypertensive and vasopressor therapy. Oral antihypertensive agents may be used once blood pressure stabilizes. Care should be taken to avoid the occurrence of hypotension.

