7.2. Less intensive blood pressure control group (control group)

The target blood pressure is 140–180 mmHg within 1 hour after randomization, and this level should be maintained for at least 48 hours. Intravenous antihypertensive therapy is preferred. Antihypertensive agents should be used intravenously when systolic pressure exceeds 180 mmHg, and discontinued when systolic pressure is \leq 150 mmHg. Oral antihypertensive agents may be used

once blood pressure stabilizes. Even if systolic pressure drops below 140 mmHg, vasopressors should not be used unless hypotension occurs.

8. Outcomes

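### Efficacy and safety are judged on a set that drops randomised patients for post-randomisation reasons, against Section 9.1's own ITT principle, so the comparison can be biased in either direction

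*Protocol*

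**What the plan says.** Protocol Section 9.1 first defines the ITT population: "This population will include all randomized patients, regardless of whether they receive the intended intervention". It then says: "A modified ITT analysis will be conducted based on the principle of the closest approach to the ITT population". From that analysis it removes patients who withdraw consent before the blood pressure intervention, and also those who "do not undergo the assigned procedure after randomization, lack endpoint data, refuse follow-up, or are lost to follow-up will be excluded". The reduced set carries the trial's conclusions: "The modified ITT analysis will be used to evaluate the effectiveness and safety of the treatment regimen".

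The full ITT set is not assigned to any analysis. The only supplement is the per-protocol set, which excludes for further reasons and also drops patients without 3-month data. Nothing in Section 9.2 brings the excluded patients back.

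Other sections that bear on the point:

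- Section 3 describes a "multicenter, prospective, randomized, endpoint-blinded, parallel-controlled trial design".
- Section 7 permits treatment to be adjusted on clinical grounds.
- Section 7.1 (intensive arm): "Intravenous antihypertensive treatment should begin immediately after randomization".
- Section 7.2 (control arm): "Antihypertensive agents should be used intravenously when systolic pressure exceeds 180 mmHg".
- Section 4.3 lists even inadvertent non-compliance as a reason to end participation. It does not say whether 90-day outcomes are still collected.

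**The concern.** Randomisation protects the comparison only while patients are analysed in the groups to which they were allocated. Every exclusion listed in Section 9.1 arises after allocation.

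- **Knowledge of the arm.** Only the endpoint is described as blinded. Treating staff must know the arm, because they titrate to different pressure targets. This is an inference from Sections 3 and 7, but a safe one.
- **Different meaning by arm.** The term for the assigned procedure is not defined. If it means starting blood pressure treatment, a control patient at 140–180 mmHg can be managed as assigned with no drug, while an untreated intensive patient can be classed as not having undergone the procedure. Patients who start treatment but miss the target stay in, because that is a per-protocol exclusion only.
- **No fixed direction.** Untreated patients may be sicker, or they may be those whose pressure fell by itself.
- **Safety.** Symptomatic haemorrhage is a primary safety outcome (Section 8.2). Loss to follow-up removes a patient from the set used for safety as well, including any haemorrhage already recorded.

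If this stands, neither a benefit nor a harm can be attributed cleanly to assignment. The protocol's background describes existing evidence as inconsistent, so the result has to be credible in both directions.

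**Working it through.** **The texts side by side.** The ITT definition keeps patients whatever treatment they received. The modified set removes patients because they did not receive it. Naming a separate modified set is not in itself a contradiction. The conflict is with the claim to approach ITT as closely as possible: a patient with a known 90-day mRS can be analysed as randomised, yet is left out.

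**The plan's own figure.** Section 5 assumes 35% against 45%, two-sided alpha 0.05, 80% power and 1:1 allocation. With pooled variance and no continuity correction:

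n = [1.96·√(2·0.40·0.60) + 0.8416·√(0.35·0.65 + 0.45·0.55)]² / 0.10² = 375.6, so 376 per arm, as stated.

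At the planned 20% loss, 0.20 × 910 = 182 patients could leave the main analysis. That leaves 364 per arm and power of about 78.8%.

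**Illustration of bias.** From the protocol: 455 randomised per arm, control rate 35%, 20% dropout. Assumed: no true effect (35% in both arms), the fraction f excluded in each arm (only the 20% is taken from the plan), and the independence rate q among the excluded. The protocol gives neither exclusion rates by arm nor outcomes of excluded patients.

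Analysed rate = (0.35 − f·q)/(1 − f). Error is the rejection probability of a two-sided pooled z-test at 1.96.

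| Case | Intensive arm | Control arm | Difference | Error |
|---|---|---|---|---|
| 1a. f = 5% vs 0%, q = 15% | (0.35 − 0.0075)/0.95 = 36.05% | 35% | +1.05 points | 6.2% |
| 1b. f = 5% vs 0%, q = 55% | (0.35 − 0.0275)/0.95 = 33.95% | 35% | −1.05 | 6.2% |
| 1c. f = 10% vs 0%, q = 15% | (0.35 − 0.015)/0.90 = 37.22% | 35% | +2.22 | 10.4% |
| 1d. f = 10% vs 0%, q = 55% | (0.35 − 0.055)/0.90 = 32.78% | 35% | −2.22 | 10.6% |
| 2. f = 10% in both, q = 10% vs 35% | (0.35 − 0.010)/0.90 = 37.78% | 35% | +2.78 | 13.1% |
| 3a. f = 20% in both, q = 25% vs 35% | (0.35 − 0.05)/0.80 = 37.5% | 35% | +2.5 | 10.8% |
| 3b. f = 20% in both, q = 15% vs 35% | (0.35 − 0.03)/0.80 = 40.0% | 35% | +5.0 | 28.6% |
| 4. same f and q in both arms | equal | equal | 0 | 5.0% |

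Case 1 covers exclusion for not being treated; cases 2 and 3 cover all reasons together. Swapping the arms in cases 2 and 3 reverses the sign.

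**Bounds without assuming q.** Suppose the analysed rates are 45% and 35%, with the same fraction excluded from each arm and their outcomes unknown. The all-randomised difference lies between the extremes where the excluded are all dependent in one arm and all independent in the other.

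- 5% excluded: +4.5 to +14.5 points.
- 10% excluded: −1 to +19 points.
- 20% excluded: 0.8·0.45 − (0.8·0.35 + 0.2) = −12 points, to (0.8·0.45 + 0.2) − 0.8·0.35 = +28 points.

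**After the change.** The case 1 bias is zero wherever the 90-day mRS is known. For missing outcomes the gain depends on how well collected data explain the missingness. If they explained half the gap in case 2, the imputed rate would be (37.78 + 10)/2 = 23.89%, and the arm rate 0.9·37.78 + 0.1·23.89 = 36.39%, leaving 1.4 points instead of 2.8. The half is an assumption.

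**The case against.** The strongest reply has four parts.

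1. **A declared modification is not a contradiction.** The modified set is named separately and its exclusions are listed openly. This is right as far as it goes. The clash that remains is with the principle of staying closest to ITT, and with the fact that the ITT set is never used.
2. **The imbalance between arms is one reading of an undefined term, and never-starters may be few.** Entry requires sustained pressure of at least 140 mmHg, and intensive treatment is to start at once. With 2% excluded from the intensive arm only, q = 15% gives (0.35 − 0.003)/0.98 = 35.4%, a bias of about 0.4 points with error about 5.2%. This stands as a caution on size. It does not justify the rule.
3. **The larger figures rest on chosen assumptions.** Cases 2 and 3 need the excluded patients' outcomes to differ between arms by 10 to 25 points. The 20% is a sample-size allowance, not a forecast of arm-related loss. Known deaths count as mRS 6 and are not missing. All of this is fair, and it is why the figures are illustrations.
4. **Imputation belongs in an SAP, and the missing-data exclusion could be applied endpoint by endpoint.** Model details can indeed sit in an SAP. The exclusion rule and the deciding set, however, are fixed in this protocol, so an SAP that did better would have to contradict it. The endpoint-by-endpoint reading does not rescue the safety analysis, because loss to follow-up is listed separately and without limit. Expedited reporting of serious events under Section 13.4 protects oversight, not the between-arm comparison.

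**Conclusion.** The concern holds and must be fixed. As written, the rule removes randomised patients from the main efficacy and safety analyses for reasons that treatment staff can influence and that may carry a different meaning in each arm. It can exclude patients with a known primary outcome and recorded events of a primary safety outcome.

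Direction and size cannot be determined from the protocol. Under the stated assumptions the false difference runs from zero, with identical selection, to about 1–2 points for non-treatment exclusions of 5–10% in one arm. It reaches 2.5–5 points at the planned 20% loss when the excluded patients' outcomes differ between arms by 10 to 20 points. The last figure is half the target effect. The conclusion rests on the exclusion rule itself and not on any one of these scenarios.

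**What to change.** - **Section 9.1, efficacy.** Make the primary analysis all randomised patients by assigned arm, excluding only those who withdraw consent to use of their data. Remove non-receipt of the assigned intervention as a reason for exclusion.
- **Section 9.1, missing 90-day mRS.** State multiple imputation using baseline data and the day-7 mRS and NIHSS already scheduled in Section 12, with a tipping-point analysis. Model details can go in the SAP. Imputation removes bias only as far as these data explain the missingness, which is why the tipping-point analysis is needed.
- **Section 9.1, safety.** Analyse symptomatic haemorrhage and death in all randomised patients with the relevant data, whatever their 90-day mRS status.
- **Section 4.3.** Clarify that non-compliance does not end outcome follow-up unless the patient refuses it.
- **Present modified ITT set.** Keep it as a sensitivity analysis.

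The cost is wording in two sections, some extra analysis, and some effort to obtain already scheduled 90-day outcomes in non-compliant patients. No new patients and no new types of visit or assessment are needed.
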